Title: The Impact of Free Fatty Acid Reduction on Vascular Function in the Metabolic Syndrome

NCT00759291

Document Date: February 28, 2008

STUDY PROCEDURES AND PROTOCOL

This study uses a randomized, placebo-controlled crossover design.

After providing informed consent, both groups will undergo an initial screening visit in the Vascular Medicine Research Center. This visit will include a comprehensive health history and physical exam and anthropomorphic data collection (height, weight, body mass index (BMI) and waist-hip ratio). Screening blood tests will be drawn to assess fasting glucose, blood count, lipid profile, glycosylated hemoglobin, and assessment of renal and hepatic function. Baseline serum insulin and nonesterified free fatty acid levels will also be drawn at this visit. An ECG will be performed.

We hypothesize that acipimox, by decreasing plasma FFA concentrations, will augment endothelium-dependent vasodilation in conduit vessels and insulin-mediated vasodilation in forearm resistance arterioles *in vivo*, whole-body insulin sensitivity, and AKT and eNOS phosphorylation in skin biopsy specimens *ex vivo*, when compared with placebo.

Subjects will be studied at 2 separate visits, 4 weeks apart, in a randomized, double-blind crossover design. Subjects will receive either acipimox 250 mg tablets orally every 6 hours, or matching placebo, for 7 days prior to and at 7 am on the morning of the study visit. Each visit will include vascular function testing and a forearm skin biopsy. Forearm blood flow will be measured in the basal state, and with insulin infusion.

Evaluation of vascular function in conduit vessels:

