signal of the ultrasound machine is connected to a computer equipped with a Data Translation frame grabber videocard. The R wave on the electrocardiogram is used as a trigger to acquire (digitize) frames. Digitized images at baseline and after intervention (e.g., reactive hyperemia, nitroglycerin) are stored on the hard drive and backed up on removable media. Acquisition and analysis of the stored images is performed using software designed for this purpose by Medical Imaging Applications. The vessel wall lumen interface is determined by derivative based edge detection following identification of the region of the anterior and posterior walls by the investigator. The maximum diameter of the vessel is then determined (59). We have found that this technique yields an interobserver variability of $0.05\pm0.16\%$ and intraobserver variability of $0.01\pm0.15\%$.

Evaluation of vascular function in forearm resistance vessels:

Each subject will be studied in the post-absorptive state, in a quiet, temperature-controlled (23°C) room. Alcohol and caffeine will be withheld for 12 hours prior to the study. In order to evaluate insulin-mediated vasodilator function in forearm resistance vessels, resistance arteriole flow will be determined before and during euglycemic, hyperinsulinemic clamp. Measurement of insulin-mediated vasodilation will be made in each study condition (placebo & drug) before and during hyperinsulinemic clamp. Forearm blood flow will be determined by venous-occlusion strain-gauge plethysmography, as described previously by this laboratory (60, 61). Forearm blood flow (FBF) will be derived from the rate of change in forearm circumference during venous occlusion and will be expressed at ml/100 ml tissue/minute. Each determination of forearm blood flow will comprise at least five separate measurements. FBF measurements will be recorded on a Hokanson AI6 physiologic recorder.

Hyperinsulinemic Clamp

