A whole-body hyperinsulinemic- euglycemic clamp will be created via an intravenous infusion of insulin. A primed constant insulin infusion of $80\text{mU}/\text{m}^2/\text{min}$ is started and continued for 120 minutes. This dose has been demonstrated to attain typical postprandial insulin concentrations, facilitating evaluation of both initial-phase and steady-state insulin-mediated vasodilation (65). Contralateral cubital vein glucose will be measured every 5 minutes to ensure a constant glucose concentration of 5.1 mmol (90 mg/dL). Adjusted dextrose 20% solution will be infused intravenously to maintain this concentration. Systemic glucose and insulin concentrations will be determined from the control arm cubital vein. Whole body insulin sensitivity will be quantified by determining M , (metabolized glucose) during the final 5 steady-state measurements. M will be calculated as the glucose infusion rate, adjusted according the method described by DeFronzo and colleagues (66).

Tissue Acquisition

Abnormalities in endothelium-dependent vasodilation have been demonstrated in humans in peripheral and coronary conduit arteries, peripheral and coronary resistance arterioles, and in skin microvessels of patients with diabetes (67-70). Therefore, we will biopsy easily accessible arm skin microvessels to determine the effects of each intervention on endothelial insulin signaling. The skin will be cleansed with betadine and draped to create a sterile field. Lidocaine 2% will be used to anesthetize a 1.2 cm ring in the arm around the biopsy site. A 6 mm bioptome will be used to obtain a

skin sample. The skin biopsy is marked for orientation and immediately frozen in liquid nitrogen and stored at –80 C for subsequent protein extraction for Western blot.

Tissue Analysis

The analyses of biopsy specimens will be performed in the laboratory of [name].

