Based on previous studies, we expect to find an absolute difference in flow-mediated, endothelium-dependent vasodilation of the brachial artery between the test agent and placebo of 3% with an estimated standard deviation of 4% (68). With a 2-sided alpha error of 0.05 and a power of 90%, 30 subjects in each group of each protocol should find at least this difference in the primary endpoint (Table 2).

Statistical methods: All descriptive data will be expressed as means \pm standard deviation. The primary endpoint of change in flow-mediated,

pathway increases eNOS phosphorylation and resultant NO production. This interpretation will be supported if multivariate linear regression analysis defines a significant positive relationship between changes in eNOS phosphorylation and vascular and/or skeletal muscle metabolic function. If endothelium-dependent (flow-mediated) or insulin-mediated vasodilation remains similar despite an intervention (acipimox), it will be interpreted as a lack of effect of the agent on endothelial-insulin signaling and vascular function. If any intervention increases vasodilation to nitroglycerin, it will be interpreted that the intervention has improved vascular smooth muscle function. If the intervention improves vascular function in both subjects with the metabolic syndrome and healthy subjects, this will be interpreted as a generalized effect, independent of the metabolic syndrome.

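### Similar insulin-mediated vasodilation is read as lack of drug effect on endothelial insulin signaling, with no check that FFA still differed between conditions during the clamp

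*Combined protocol and SAP*

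**What the plan says.** The hypothesis in Study Procedures and Protocol runs through FFA: acipimox, "by decreasing plasma FFA concentrations, will augment endothelium-dependent vasodilation in conduit vessels and insulin-mediated vasodilation in forearm resistance arterioles", is expected to outperform placebo. Whole-body insulin sensitivity and AKT/eNOS phosphorylation are further named outcomes. Subjects take acipimox "or matching placebo, for 7 days prior to and at 7 am on the morning of the study visit".

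The section on forearm resistance vessels states: "Measurement of insulin-mediated vasodilation will be made in each study condition (placebo & drug) before and during hyperinsulinemic clamp". Under Hyperinsulinemic Clamp, the insulin infusion "is started and continued for 120 minutes", with no difference between conditions. The insulin dose is said to "attain typical postprandial insulin concentrations, facilitating evaluation of both initial-phase and steady-state insulin-mediated vasodilation". The insulin-sensitivity measure, M, comes from the last five steady-state readings. The analytes named for the clamp are glucose and insulin: "Systemic glucose and insulin concentrations will be determined from the control arm cubital vein".

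The only FFA draw with a stated time is at screening. The assay section describes an FFA assay without sampling times, but has the assayists blinded to treatment.

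The Data interpretation text has two relevant rules. If flow-mediated dilation (FMD) is restored on acipimox, FFA is taken to impair endothelial insulin signaling. If FMD or insulin-mediated vasodilation is similar in the two conditions, "it will be interpreted as a lack of effect of the agent on endothelial-insulin signaling and vascular function". Neither rule refers to the FFA levels achieved. The sample size rests on FMD alone.

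**The concern.** A null result on a hypothesis that works through FFA can be read in two ways. If FFA differed between conditions when the endpoint was measured, the null speaks to FFA reduction itself. If it did not, the null speaks only to what the preceding 7 days left behind. The plan neither checks which case applies nor limits its conclusion.

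The clamp makes this a practical worry, because insulin is generally understood to suppress lipolysis. If FFA falls on placebo during the infusion, the placebo condition moves toward the acipimox condition while insulin-mediated vasodilation is being recorded. A similar response could then be reported as evidence against the drug and the mechanism when the contrast had largely gone.

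The word joining the two endpoints in the null rule adds to the problem: a null on either one is enough to trigger the negative conclusion, even beside a positive result on the primary endpoint.

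**Working it through.** **1. What is tied to the clamp.** Setting the sections side by side:

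| Item | Stated in the plan |
|---|---|
| Insulin infusion | Same in both conditions, 120 minutes |
| Insulin-mediated vasodilation | Before and during the infusion, both conditions |
| Glucose, insulin | Named for the clamp |
| FFA | Timed at screening only; on-treatment samples implied by the blinding, timing not given |
| Effect of insulin on FFA | Not mentioned |
| Effect size or SD for insulin-mediated vasodilation | Not given |

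**2. The plan's own power figure (FMD).** Inputs from the sample-size text and Table 2: difference 3%, SD 4%, 30 subjects per group, two-sided alpha 0.05, paired design. Taking the SD as that of within-subject differences, power is the probability that a noncentral t with 29 degrees of freedom and noncentrality (3/4) × √30 = 4.11 exceeds the critical value in absolute size. This gives 0.978, against .98 in Table 2. The other eight cells also agree to within 0.01. There is no corresponding calculation for insulin-mediated vasodilation.

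**3. How much FFA contrast might remain (assumptions throughout).** Set basal placebo FFA to 1. Let a be the acipimox level as a fraction of that, and s the fraction by which insulin lowers placebo FFA. If acipimox FFA does not fall further, the contrast goes from 1 − a to (1 − s) − a, and the share remaining is (1 − s − a)/(1 − a).

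- a = 0, s = 0.5, 0.7 or 0.9: share 0.50, 0.30 or 0.10.
- a = 0.30, s = 0.5: 0.20/0.70 = 0.29.
- a = 0.30, s = 0.7: 0/0.70 = 0.
- s = 0: share 1.

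Placebo FFA left under insulin is therefore not the same thing as contrast left; the two agree only when a = 0. The documents give neither a nor s.

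**4. What that could do to the clamp endpoint (illustration).** Assume insulin-mediated vasodilation has the FMD standardised effect, 0.75, and that its effect is proportional to the share f of FFA contrast remaining. With n = 30 the noncentrality is f × 4.11:

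| f | Noncentrality | Power |
|---|---|---|
| 1.00 | 4.11 | 0.98 |
| 0.75 | 3.08 | 0.85 |
| 0.50 | 2.05 | 0.51 |
| 0.25 | 1.03 | 0.17 |
| 0.10 | 0.41 | 0.07 |

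The case f = 0.29 falls between 0.17 and 0.51.

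**5. Discordant results.** Suppose FMD is restored and insulin-mediated vasodilation is similar. The positive rule concludes that FFA impairs endothelial insulin signaling and that relieving it helped. The null rule, met by its second limb, concludes that the agent affects neither signaling nor vascular function. Both apply to the same data, and the text does not say which prevails. This pattern is what one would expect if FFA reduction works but the contrast is lost under insulin.

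**The case against.** The strongest case against runs as follows. The premise that insulin lowers FFA on placebo is nowhere in the documents, which give no size or time course. The randomized comparison is 7 days of treatment plus a study-morning dose, so an effect carried over from that exposure is much of what the design tests, and the null rule speaks of the agent, not of FFA at a given minute. The assayists' blinding to treatment implies that some on-treatment FFA will be measured. The primary endpoint, FMD, needs no insulin.

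All of this stands, and it limits the point. A reader might infer that placebo stops being a higher-FFA comparator once insulin starts, so that a null clamp result would necessarily be misread. The documents do not support that. Suppression takes time and may be incomplete in insulin-resistant subjects, an initial phase is also to be evaluated, and a null may be a true lack of effect. A reader might also infer that the null rule covers M; it names only the two vasodilation endpoints.

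What the objection does not answer is that the rule is unconditional, that no FFA sample is tied to the clamp, and that the two interpretation rules can collide. None of these depends on how strongly insulin suppresses FFA.

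**Conclusion.** The point holds in limited form. Similar insulin-mediated vasodilation cannot by itself carry the conclusion the plan assigns to it, because it could reflect reduced FFA contrast during the clamp, low precision on an endpoint that was never sized, or true lack of effect, and the specified data may not distinguish these. The contradiction between the two interpretation rules follows from the text alone.

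The size is not determinable from the documents. The fall in power from 0.98 to 0.51 or 0.07 rests on three assumptions: the FMD standardised effect applies to this endpoint, its effect tracks concurrent FFA, and half or a tenth of the contrast remains. If the 7-day exposure has a lasting effect, the loss would be smaller. M is read at steady state in the same clamp and deserves the same caution, as an extension of the rule. The FMD power calculation is unaffected. The order of FMD and clamp within a visit is not stated.

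**What to change.** - At both visits, assay FFA just before the insulin infusion and at clamp steady state, using the existing sampling line and the FFA assay already planned.
- In Data interpretation, give insulin-mediated vasodilation its own rule, separate from FMD, so that a null clamp result does not override a positive FMD result. State how discordant results will be read.
- Report the treatment difference in insulin-mediated vasodilation with a confidence interval, separately for initial phase and steady state, alongside the between-condition FFA difference during the clamp. The interval should replace the judgement that responses are similar.
- If FFA did not differ during the clamp, state that an effect of concurrent FFA reduction was not tested, instead of concluding lack of effect. Interpret M with the same caution.

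The cost is a few plasma aliquots and assays per visit, some redrafting, and a more qualified negative conclusion. The exact number of extra assays depends on on-treatment samples whose timing the plan does not give. No extra visit is needed. Samples not drawn during the clamp cannot be recovered later.

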Immunodetection: Serial 4 µM sections of skin biopsy sections are deparaffinized, hydrated, and serially incubated in citrate buffer, H₂O₂, blocking solution, primary antibody, and appropriate secondary antibody, with intervening washes. The ABC biotin/avidin method with Nova Red substrate is utilized for immunodetection (Vector Labs). Primary antibodies include: total Akt (Cell Signaling), phospho-specific Akt (Ser 473, Cell Signaling), total eNOS (Transduction Labs), and phospho-specific eNOS (Ser 1177, Cell Signaling). When available, blocking peptide is incubated with primary antibody in a separate section to ensure specificity of staining. If blocking peptide is not available, additional sections are incubated without primary antibody. To ensure localization of identified signal in vascular cells, additional sections will be processed for immunofluorescence and colocalization with primary antibodies directed against the endothelium-specific von Willebrand factor (Santa Cruz Biotechnology). Images will be viewed using an AX70 Olympus Microscope with Phase 3 Imaging System (Image Pro 4.0 software) or the Zeiss LSM-410 Invert Laser Scan confocal microscope with imaging software (Matrox Image-Series Utilities).

Assays for markers of inflammation, insulin, free fatty acids

Plasma samples from insulin resistant and healthy subjects will be assayed for high sensitivity CRP (hsCRP), tumor necrosis factor-α (TNF-α), and interleukin-6 (IL-6) using the respective ELISA kits (Sigma; Endogen, Woburn, MA; BenderMedSystems; Vienna, Austria). Plasma insulin concentration will be measured using an Immunoenzymatic Sandwich Assay (Beckman Coulter, Inc.). Acrylodan-labeled Intestinal Fatty Acid Binding Protein (ADIFAB), a fluorescent molecule, will be used to assay the concentration of free fatty acids. The assay is accurate to about 1nM (72). All assays will be performed in duplicate by investigators blinded to the status of the subject (metabolic syndrome or control) and treatment.

BIOSTATISTICAL ANALYSIS

Statistical Analysis

Sample size calculation: All specified protocols employ a randomized, placebo-control cross-over design. Given the paired-design, the sample sizes have been calculated using estimates of the difference in flow-mediated, endothelium-dependent vasodilation after placebo and active treatment.

Table 2: Calculated Power For a Given Effect Size and Standard Deviation
Standard Deviation

Treatment Effect	3.5%	4.0%	4.5%
2.5%	.97	.91	.84

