3.0%	.99	.98	.94
3.5%	1.0	.99	.98

endothelium-dependent vasodilation (i.e., the change in brachial artery vasodilation) between active therapy and placebo, will be assessed using repeated measures ANOVA (73). All analyses will employ the intention-to-treat principle. The treatment “order effect” will be explored by examining the interaction between treatment group (e.g. acipimox vs. placebo) and sequence of treatment (placebo first vs. active therapy first).

Baseline characteristics of treatment and control patients will be compared using Student’s t-test or non-parametric tests, depending on the distribution of the data. To examine whether the active therapy has similar effects on flow-mediated vasodilation between healthy subjects and those with the metabolic syndrome, we will test the interaction between treatment group and the metabolic syndrome (yes/no). In secondary analyses, we will assess the effects of active therapy on eNOS phosphorylation, insulin sensitivity, and plasma inflammatory markers such as CRP, IL-6, and TNF- α . We will assess the relationship between the change in eNOS phosphorylation and changes in endothelium-dependent vasodilation using linear regression analyses, controlling for age, and gender. Likewise, we will examine the relationship between changes in insulin-mediated vasodilation and insulin-sensitivity associated with active treatment. Multiple analysis of variance (MANOVA) will be used to examine the main and interaction effects of categorical variables on multiple dependent variables, and multiple analysis of covariance (MANCOVA) for continuous independents. Thus, in the analyses, we can include vascular function and other outcomes simultaneously as dependent variables in the models. If the dependent variables are uncorrelated with each other, repeated measure ANOVA for each dependent variable will be employed.

Data interpretation: Vascular function will be determined after each intervention. Each intervention will be studied individually. If flow-mediated vasodilation is restored after an intervention (acipimox) compared with placebo, it will be interpreted that FFA impairs endothelial insulin signaling and decreases endothelium-dependent vasodilation. This interpretation will be confirmed by cutaneous tissue testing. If eNOS serine₁₁₇₇ phosphorylation is increased after an intervention compared to placebo, it will be interpreted that improved activation of the PI3-kinase

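### The null rule reads unchanged vasodilation as lack of effect of acipimox, without requiring that FFA was lowered or that the confidence interval excludes a relevant effect

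*Combined protocol and SAP*

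**What the plan says.** The hypothesis under Study Procedures and Protocol is pharmacological and names its mediator: "We hypothesize that acipimox, by decreasing plasma FFA concentrations, will augment endothelium-dependent vasodilation". Tablets are taken every 6 hours "for 7 days prior to and at 7 am on the morning of the study visit". The text does not say how intake is checked, or how a subject who stops or misses doses is handled.

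Under Statistical methods, "All analyses will employ the intention-to-treat principle". The term is not defined further, and no second analysis set is named.

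Data interpretation then gives two rules. If flow-mediated dilation (FMD) is restored, "it will be interpreted that FFA impairs endothelial insulin signaling and decreases endothelium-dependent vasodilation", and skin tissue testing is to confirm that reading. If flow-mediated or insulin-mediated vasodilation stays similar, "it will be interpreted as a lack of effect of the agent on endothelial-insulin signaling and vascular function". The null rule has no confirming step and does not define what counts as similar.

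The assay section does plan an FFA measurement: a fluorescent binding protein "will be used to assay the concentration of free fatty acids", read blind to treatment. FFA is not listed among the secondary analyses, and neither rule refers to it.

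**The concern.** Intention-to-treat estimates what assignment to acipimox does. The null rule turns that estimate into a statement about what the drug does to a signalling pathway. The step is sound only if the drug was taken, FFA fell, and the data were precise enough to rule out an effect worth finding. The rule asks for none of these.

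A subject who stopped taking tablets but still attends is, in the ordinary meaning of intention-to-treat, analysed as on acipimox. The crossover does not remove the resulting dilution, because that subject contributes an expected within-subject difference near zero. The biopsies would not reveal the problem either: in someone off drug, unchanged eNOS phosphorylation is what one would expect. A reader of the final report could not tell an inactive drug from an untaken one, and dosing information not collected at the visits may be unrecoverable later.

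**Working it through.** **Inputs from the documents.** FMD difference 3% and SD 4% (sample size text). "With a 2-sided alpha error of 0.05 and a power of 90%, 30 subjects in each group of each protocol". Paired design, so the SD is taken as that of the within-subject difference.

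**Inputs assumed.** A share p of subjects is off drug at the acipimox visit but still measured, with no drug effect; the others have the full 3%. The documents give no value for p. 'Similar' is taken to mean a non-significant two-sided test at 0.05.

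**Step 1: reproduce the plan's figure.** Power of a paired t-test from the noncentral t, with 29 degrees of freedom and noncentrality (difference / SD) × √30. For 3% and 4% this is 0.75 × 5.477 = 4.108, giving power 0.978. Table 2 states .98. All nine cells of Table 2 reproduce to within 0.01, so the method matches the plan's.

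**Step 2: dilute the effect.** Expected intention-to-treat difference = 3 × (1 − p). Power is given with the SD held at 4%, and with the larger SD that results from mixing subjects on and off drug, √(16 + 9p(1 − p)).

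| Off drug (assumed) | Expected difference | Mixture SD | Power, SD 4% | Power, mixture SD | Chance of a null |
|---|---|---|---|---|---|
| 0% | 3.0% | 4.00 | 0.978 | 0.978 | 2% |
| 10% | 2.7% | 4.10 | 0.947 | 0.936 | 5–6% |
| 20% | 2.4% | 4.18 | 0.888 | 0.860 | 11–14% |
| 30% | 2.1% | 4.23 | 0.794 | 0.748 | 21–25% |
| 40% | 1.8% | 4.26 | 0.664 | 0.609 | 34–39% |

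Power falls below the stated 90% at about 15% off drug (mixture SD) or 18% (SD 4%).

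**Step 3: imprecision, with full adherence.** The 95% half-width at n = 30 and SD 4% is 2.045 × 4 / √30 = 1.49 points. An estimate of 1.2% is then non-significant, with interval 1.2 ± 1.49, or −0.29% to 2.69%. That includes 2.5%, an effect for which Table 2 reports power of .91. The rule would still call this a lack of effect.

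**Step 4: what a 3% margin would do.** At n = 30 and SD 4%, the largest non-significant estimate is 1.49%, with upper limit 2 × 1.494 = 2.99%. Every non-significant result therefore already excludes 3%. A margin of exactly 3% restricts nothing unless the SD is larger or the group smaller; at n = 24 the half-width is 1.69 and the upper limit can reach 3.38%.

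**Step 5: the second outcome.** Insulin-mediated vasodilation is measured as forearm blood flow in ml/100 ml tissue/minute. The 3% figure is an FMD difference and cannot serve as its margin. The documents give no design difference for that outcome.

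**The case against.** The strongest reply is that the size depends wholly on an assumed stopping rate. The course lasts only 7 days, and the paired design has enough reserve to keep the stated 90% power up to about 15% off drug. The all-or-nothing model is also severe. If 30% of subjects were affected but kept half the effect (again an assumption), the mean would be 3 × 0.7 + 1.5 × 0.3 = 2.55%, the SD √(16 + 2.25 × 0.21) = 4.06, and the power 0.91. The table covers one group of 30; if the effect were common to both groups and they were pooled (n = 60), power at 30% off drug would be 0.97 to 0.98. All of this stands, and it limits the size of the dilution. It does not supply the missing conditions in the rule.

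A reader might infer that dosing is unsupervised or that adherence will be poor. The documents say neither. They are silent on accountability, and they refer to a preliminary results section and to other protocols that are not included, so silence is weak evidence that no check was planned.

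A reader might also infer that intention-to-treat is the wrong analysis or that the sample size is wrong. Neither follows: intention-to-treat is a sound primary analysis, and Table 2 reproduces.

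Finally, the rule speaks of the agent. Calling a null result evidence against the FFA mechanism goes beyond its literal words, although the positive rule does draw a conclusion about FFA.

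**Conclusion.** The concern holds as a fault of interpretation and needs no particular stopping rate. As written, a null result from any cause becomes a statement that acipimox does not affect endothelial insulin signalling, and the plan's own FFA assay is not used to check it. Imprecision alone can produce the same statement with full adherence.

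The size of the adherence component is conditional. With a 3% effect on drug, none off drug, SD 4% and one group of 30, the chance of a false null rises from about 2% to 5–6% at 10% off drug, 11–14% at 20% and 21–25% at 30%. At 10% or less the loss is modest. The change is worth making because it is cheap and the exposure data must be collected at the visits.

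**What to change.** Keep intention-to-treat as the primary analysis, and make four changes.

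1. State that FFA is measured at both study visits at the same specified time point, and report it by treatment. The assay is already planned.
2. Record, before unblinding, the doses taken over the preceding 7 days and whether the 7 am dose was taken.
3. Pre-specify a supportive on-treatment analysis of FMD and insulin-mediated vasodilation, using the same blinded dosing criterion in both periods.
4. Replace the null sentence with: *will be interpreted as no detected effect of assignment to acipimox; lack of effect of the agent will be considered only if FFA was lower on acipimox than on placebo and the 95% confidence interval for the FMD difference excludes a pre-specified relevant effect (no larger than the 3% design difference), with a separate pre-specified margin in forearm blood flow units for insulin-mediated vasodilation.*

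The FMD margin should be set below 3% if it is to restrict anything at the planned size and SD (step 4). A lower mean FFA on acipimox can coexist with a minority off drug, so individual FFA changes and the on-treatment result should be shown beside the primary result.

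The cost is a line on the visit form, one FFA summary, one supportive analysis and a reworded sentence. The on-treatment set is smaller and selected after randomisation, so it can only support the primary result. The null claim also becomes harder to make.

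### Improvement in both groups is to be read as an effect independent of the metabolic syndrome, without using the planned interaction and although two within-group results cannot show this

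*Combined protocol and SAP*

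**What the plan says.** Two places in the Biostatistical Analysis section deal with how the drug effect compares between healthy subjects and those with the metabolic syndrome.

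- **Statistical methods** plans a test of the interaction between treatment and metabolic syndrome status. Its purpose is stated: "To examine whether the active therapy has similar effects on flow-mediated vasodilation between healthy subjects and those with the metabolic syndrome". The outcome named is flow-mediated vasodilation.
- **Data interpretation**, last sentence, gives a rule for the conclusion. It applies if vascular function is better on the drug "in both subjects with the metabolic syndrome and healthy subjects, this will be interpreted as a generalized effect, independent of the metabolic syndrome". The rule mentions no interaction, no estimate of the difference between groups, no confidence interval and no margin for calling effects similar.

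The sample size paragraph asks for "30 subjects in each group of each protocol" and is built on the within-subject comparison of drug with placebo. No power or precision is given for the comparison between groups.

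**The concern.** Whether an effect is present in each group and whether it is the same size in each group are different questions. The rule answers the second with evidence on the first. The plan has the right tool, the interaction, but the sentence that fixes the conclusion does not refer to it. The plan therefore holds two routes to a statement about dependence on the syndrome, and nothing says which one governs.

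The trial is about the metabolic syndrome, so whether the effect depends on it is one of the main things a reader will want to know. Followed as written, the plan could report no dependence when the effect in healthy subjects is half as large, or even when its own interaction test is significant. The rule also speaks of vascular function in general, whereas the named interaction covers flow-mediated vasodilation only.

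**Working it through.** **Inputs from the documents.** 30 subjects per group; two-sided alpha .05; planned effect 3% and SD 4% (Sample size calculation); SD range 3.5 to 4.5% (Table 2).

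**Assumptions.** The plan gives no group-specific effects, so they are varied here. The SD is taken to be the same in both groups. The plan does not define improvement, so it is read as a within-group paired t-test with two-sided p<.05.

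**Step 1: reproduce Table 2.** Power of a paired t-test, from the noncentral t with 29 df and noncentrality effect × √30 / SD. For 3% and SD 4%, the noncentrality is 3 × 5.477 / 4 = 4.11 and the power is .978; Table 2 has .98. At SD 3.5 and 4.5 the results are .995 and .942, against .99 and .94. All nine cells agree to within about a point. The tabulated SD is therefore that of the within-subject difference in one group of 30.

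**Step 2: how often the rule fires when effects differ.** The groups are independent, so the chance that both are significant is the product of the two powers. For 3% and 1.5% at SD 4: .978 × .510 = .499.

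| True effects (syndrome / healthy) | SD 3.5 | SD 4 | SD 4.5 |
|---|---|---|---|
| 3% / 3% | – | .96 | – |
| 3% / 2% | .85 | .74 | .61 |
| 3% / 1.5% | .62 | .50 | .40 |
| 3% / 1% | .33 | .26 | .20 |

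With larger effects the rule hardly discriminates. At SD 4, both groups are significant with probability .98 for 6% against 3%, compared with .96 for equal effects of 3%.

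**Step 3: precision of the interaction.** The estimate is the difference between the two groups' mean paired differences, with SE = SD × √(2/30) and 58 df.

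- At SD 4 the SE is 4 × .2582 = 1.03 points.
- The 95% CI half-width is t(.975, 58) × SE = 2.07 points (1.81 at SD 3.5, 2.33 at SD 4.5).
- Power for a 1.5-point difference is .30 (.37 and .25).
- The difference detectable with 80% power is 2.94 points (2.57 and 3.31), about the whole planned effect.

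**Step 4: the rule and the interaction together (simulation).**

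| Scenario | Both groups significant, interaction not | Both groups and interaction significant |
|---|---|---|
| 3% / 1.5%, SD 3.5 | .49 | .13 |
| 3% / 1.5%, SD 4 | .44 | .06 |
| 3% / 1.5%, SD 4.5 | .37 | .03 |
| 6% / 3%, SD 4 | .18 | .79 |

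In the last column the rule says independent while the plan's own test says the effects differ. In the middle column neither the rule nor the interaction p-value signals the difference.

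**The case against.** The strongest reply is that the phrase only explains the word generalized: the effect does not require the syndrome and is not confined to it. Improvement in both groups does support that. On this view the interaction answers whether the sizes are similar, the interpretation sentence answers whether the effect is present in both, and only a cross-reference is missing. The word generalized alone would indeed be acceptable. The added claim of independence goes further, and a reader will take it as a statement about size.

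Statistical methods also plans MANOVA with interaction effects of categorical variables on several outcomes, which could extend the comparison beyond flow-mediated vasodilation. It may, but that sentence does not name the syndrome interaction, and nothing ties it to the interpretation rule.

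Three further points stand and limit the finding:

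- The p<.05 criterion for improvement is the natural reading of an undefined term, and the group-specific effects are illustrative.
- In the halved scenario the rule does not fire in half of trials. Outright conflict with the interaction test occurs in about 6%, against about 4% when both true effects are 3% at SD 4.
- The 44% of trials with a non-significant interaction reflect limited power at this sample size, which rewording does not change. The interaction model would still yield an estimate of the difference, and that is why the conclusion should rest on the estimate.

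**Conclusion.** The concern holds. The interaction is planned, so no analysis of flow-mediated vasodilation is missing; the fault is in the rule for interpreting it. With 30 per group, a healthy-subject effect of half the planned 3% would be declared independent of the syndrome in 50% of trials (40 to 62% over the Table 2 SDs). At 6% against 3% and SD 4, the rule would contradict a significant interaction in 79%. These figures rest on equal SDs, within-group significance as the meaning of improvement, and assumed group effects. The logical point rests on none of them. The primary comparison of drug with placebo is not affected, but a prespecified conclusion would be unsupported, so the sentence should be changed.

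**What to change.** Replace the independence claim with wording such as: *effect seen in both groups; difference between groups X (95% CI)*. Base any statement about dependence on the syndrome on the interaction estimate and its 95% CI, for each vascular measure the sentence is meant to cover, and state that a non-significant interaction will not be read as equality. As a minor clarification, say that the drug-placebo contrast is made within each group, as the sample size paragraph implies.

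The cost is one reworded sentence and a short clarification, plus one added estimate for each vascular measure other than flow-mediated vasodilation. No new subjects, visits or data are needed. The price is a weaker claim of generality: the interval for the group difference will be about ±2 points, which is what 30 per group can support.
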